### **6.11.2. Prohibited Medications and Non-Drug Therapies**

Use of any of the following drugs from screening until 7 days after the last dose of study treatment is prohibited:

- Strong inhibitors of CYP2C8 (e.g., gemfibrozil)
- Strong inducers of CYP2C8 (e.g., rifampin/rifampicin)

Use of the following drug from 8 weeks prior to screening until the last dose of study treatment in ESA non-users and during study treatment in ESA user is prohibited.

- Erythropoietin (e.g., epoetin/darbepoetin alfa/ epoetin beta pegol)

Note: excluding epoetin beta pegol (brand name: Mircera® Injection Syringe) supplied by GSK.

## **6.12. Supplemental Iron Therapy**

Supplemental iron therapy will be administered according to the Guidelines for Renal Anemia [The Japanese Society for Dialysis Therapy, 2008] if ferritin is  $\leq 100$  ng/mL and TSAT is  $\leq 20\%$ . The investigator (or subinvestigator) can choose the route of administration and dose of prescription iron.

## **7. Study Assessments and Procedures**

Protocol waivers or exemptions are not allowed with the exception of immediate safety concerns. Therefore, adherence to the study design requirements, including those specified in the Time and Events Table, are essential and required for study conduct.

### **7.1. Time and Events Table**

The time and events tables for the entire study and PK assessment are presented as Table 14 and Table 15, respectively. To allow scheduling flexibility, study visits may occur within a window of  $\pm 7$  days on Day 1 scheduled 4 weeks after screening, within a window of  $\pm 3$  days at Week 2 (Cohort 3 only) and Week 4, and within a window of  $\pm 5$  days for the rest of the study. However, subjects receiving the control epoetin beta pegol every 2 weeks should attend study visits, including those only for study treatment, within a window of  $\pm 3$  days. Visit days are counted from Day 1.

Table 14 Time and Events Table

Phase	Screening 	Treatment															Follow-up	
Week	-4	Day 1	2 	4	8	12	16	20	24	28	32	36	40	44	48	52	Early withdrawal 	4 weeks after 52 or withdrawal
Permissible range (days)	±7	-	±3	±3	±5	±5	±5	±5	±5	±5	±5	±5	±5	±5	±5	±5	-	±7
Informed consent	X																	
Inclusion/exclusion criteria	X	X																
Medical history, demography, height, weight	X																	
Registration with IWRS	X	X	X	X	X	X	X	X	X	X	X	X	X	X	X	X	X	X
Study medication dispensing 		X	X	X	X	X	X	X	X	X	X	X	X	X	X			
Study treatment compliance			X	X	X	X	X	X	X	X	X	X	X	X	X	X	X	X
Vital signs	X	X		X			X			X			X			X	X	X
Ophthalmology 		↔				↔										↔	↔	↔
ECG	X									X							X	
HemoCue Hgb	X	X	X	X	X	X	X	X	X	X	X	X	X	X	X	X	X	
Hematology	X	X	Only Hgb	X	Only Hgb	X	Only Hgb	X	Only Hgb	X	Only Hgb	X	Only Hgb	X	Only Hgb	X	X	X
Clinical chemistry	X	X		X			X			X			X			X	X	X
Urinalysis (ND subjects only)	X	X							X							X		X
Pregnancy test (urine or serum hCG) 	X	X		X			X			X			X			X	X	X
Estradiol, FSH 	X																	
PK 						X			X									
Ferritin, TSAT	X	X		X			X			X			X			X	X	
Serum iron, TIBC, UIBC, serum transferrin, hepcidin			X		X			X			X			X		X	X	
iPTH		X								X						X		
HR-QoL			X				X			X						X	X	
Genetics sample 		X																
Adverse event assessment 		↔														↔		
Review Concomitant Medications		↔																

1. In Cohort 1 and Cohort 3, ESA non-users randomized to the epoetin beta pegol group will start treatment with epoetin beta pegol at a dose of 25 µg once every 2 weeks. For these subjects, specified examinations will be performed at Week 2 (Cohort 3 only) and every 4 weeks after Week 4, and no study-related assessments will be necessary at study visits only for study treatment [e.g., Week 2 (Cohort 1 only), Week 6, Week 10] (see Section 6.4.2). It should be noted that subjects receiving epoetin beta pegol once every 2 weeks should attend study visits within a window of ±3 days.
2. If a subject visit the study site only to receive study medication, only registration with the IWRS, study medication dispensing, and study medication compliance will be required.
3. Ophthalmology exams should be conducted at the following time points.

- Screening: anytime after consenting and prior to first dose of study medication (Day 1)
- Week 12: window from weeks 10-14 (inclusive)
- End of study: window from weeks 48-52 (inclusive)
- Early study medication discontinuation: withdrawal eye exam as close to the last dose as possible (the repeat exams are not required if one has been performed within the 2 prior weeks).

4. Performed in females of childbearing potential: serum pregnancy test will be performed if urine pregnancy test is not feasible.

5. Measured in female subjects only to determine the menopausal status (see Section 5.1.)

6. See Table 15.

7. Informed consent for optional Genetic research should be obtained before collecting a sample (see Section 7.6.).

8. See Section 7.4.1.1..

9. Re-screening subjects who meet all the following conditions are allowed to use the results of the latest ophthalmology exam and not required to undergo the rescreening ophthalmology exam, at the discretion of the investigator.

- Subjects had no findings that deem re-exams within 3 months at the latest screening ophthalmology exam.
- Subjects had no new eye-related symptoms or complaints until the rescreening following the latest screening ophthalmology exam.
- The latest screening ophthalmology exam was performed within 3 months prior to Day 1 scheduled at the rescreening.

10. All ND subjects randomized to Cohort 3 will undergo assessment scheduled for Week 2 visit.

11. For withdrawn subjects, specified assessments should be done wherever possible.

**Table 15 Blood Sampling Schedule for Pharmacokinetics (Only Subjects in GSK1278863 Group)**

PK sample	Week 12 	Week 24 
Blood sampling timing 	1, 2, 3, and 4 h after administration of GSK1278863	

Subjects must take the study medication with regard to blood sampling time. Subjects will record the date and time of the last two study medication doses taken prior to blood sampling in the medication diary. Preferably, there should be an interval of at least 12 h between these two doses.

1. Blood sampling should be completed within +/- 30 min of the planned collected time.
2. Blood sampling not performed at this visit may be postponed until the following visits.

## 7.2. Screening and Critical Baseline Assessments

Cardiovascular medical history/risk factors will be assessed (documented in the eCRF) at baseline.

In addition, the following demographic information will be collected:

- Year of birth
- Gender
- Race and ethnic
- Medical history/treatment history/family history will be assessed in relation to the inclusion/exclusion criteria (Section 5.).

Full details of baseline assessments are provided in Table 14.

## 7.3. Efficacy

Efficacy will be assessed according to the Time and Event Table (Table 14).

Hgb concentrations measured by the central laboratory will be mainly used for efficacy assessment (see Section 7.4.7.).

GSK will supply a point-of-care Hgb analyzer (HemoCue) to each site for rapid and convenient measurement of Hgb and to ensure consistency of Hgb measurements across all sites participating in the study. Assessment for Hgb concentrations via HemoCue will be used for eligibility (Section 5.1.), withdrawal (Section 5.4.), and dose adjustment criteria (Section 6.4.).

In addition, assessments of iron metabolism parameters and measures of CKD progression (e.g., eGFR) used for efficacy assessment are outlined with specific procedures in Section 7.4.7..

## 7.4. Safety

Planned time points for all safety assessments are listed in the Time and Events Table (Table 14).

Additional time points for safety tests (such as vital signs, physical exams and laboratory safety tests) may be added during the course of the study based on newly available data to ensure appropriate safety monitoring.

### 7.4.1. Adverse Events (AE) and Serious Adverse Events (SAEs)

The definitions of an AE or SAE can be found in Section 12.6. Appendix 6.

The investigator and their designees are responsible for detecting, documenting and reporting events that meet the definition of an AE or SAE.

**7.4.1.1. Time period and Frequency for collecting AE and SAE information**

- AEs and SAEs will be collected from the start of Study Treatment until the follow-up contact (see Section 7.4.1.3.), at the timepoints specified in the Time and Events Table (Table 14).
- Medical occurrences that begin prior to the start of study treatment but after obtaining informed consent may be recorded on the Medical History/Current Medical Conditions section of the CRF.
- Any SAEs assessed as related to study participation (e.g., protocol-mandated procedures, invasive tests, or change in existing therapy) or related to a GSK product will be recorded from the time a subject consents to participate in the study up to and including any follow-up contact.
- All SAEs will be recorded and reported to GSK within 24 hours, as indicated in Section 12.6. Appendix 6.
- Investigators are not obligated to actively seek AEs or SAEs in former study subjects. However, if the investigator learns of any SAE, including a death, at any time after a subject has been discharged from the study, and he/she considers the event reasonably related to the study treatment or study participation, the investigator must promptly notify GSK.

NOTE: The method of recording, evaluating and assessing causality of AEs and SAEs plus procedures for completing and transmitting SAE reports to GSK are provided in Section 12.6. Appendix 6.

**7.4.1.2. Method of Detecting AEs and SAEs**

Care will be taken not to introduce bias when detecting AEs and/or SAEs. Open-ended and non-leading verbal questioning of the subject is the preferred method to inquire about AE occurrence. Appropriate questions include:

- “How are you feeling?”
- “Have you had any (other) medical problems since your last visit/contact?”
- “Have you taken any new medicines, other than those provided in this study, since your last visit/contact?”

**7.4.1.3. Follow-up of AEs and SAEs**

After the initial AE/SAE report, the investigator is required to proactively follow each subject at subsequent visits/contacts. All SAEs, and non-serious AEs of special interest (as defined in Section 7.4.2.) will be followed until resolution, until the condition stabilizes, until the event is otherwise explained, or until the subject is lost to follow-up (as defined in Section 5.4.). Further information on follow-up procedures is given in Section 12.6. Appendix 6..

**7.4.1.4. Cardiovascular and Death Events**

For any cardiovascular events detailed in Section 12.6. Appendix 6 and all deaths, whether or not they are considered SAEs, specific Cardiovascular (CV) and Death sections of the CRF will be required to be completed. These sections include questions regarding cardiovascular (including sudden cardiac death) and non-cardiovascular death.

The CV CRFs are presented as queries in response to reporting of certain CV MedDRA terms. The CV information should be recorded in the specific cardiovascular section of the CRF within one week of receipt of a CV Event data query prompting its completion.

The Death CRF is provided immediately after the occurrence or outcome of death is reported. Initial and follow-up reports regarding death must be completed within one week of when the death is reported.

#### **7.4.1.5. Regulatory Reporting Requirements for SAEs**

Prompt notification by the investigator to GSK of SAEs and non-serious AEs related to study treatment (even for non- interventional post-marketing studies) is essential so that legal obligations and ethical responsibilities towards the safety of subjects and the safety of a product under clinical investigation are met.

GSK has a legal responsibility to notify both the local regulatory authority and other regulatory agencies about the safety of a product under clinical investigation. GSK will comply with country specific regulatory requirements relating to safety reporting to the regulatory authority, Institutional Review Board (IRB)/Independent Ethics Committee (IEC) and investigators.

Investigator safety reports are prepared for suspected unexpected serious adverse reactions according to local regulatory requirements and GSK policy and are forwarded to investigators as necessary.

An investigator who receives an investigator safety report describing a SAE(s) or other specific safety information (e.g., summary or listing of SAEs) from GSK will file it with the IB and will notify the IRB/IEC, if appropriate according to local requirements.

#### **7.4.2. Adverse Events of Special Interest**

The investigator (or subinvestigator) or designee will be responsible for detecting, documenting, and reporting any AEs of special interest listed below. These events have been identified based on the known safety profiles of ESAs, theoretical or potential risks based on the mechanism of action of GSK1278863, and findings from completed nonclinical studies of GSK1278863.

- Thrombosis and/or tissue ischemia secondary to excessive erythropoiesis
- Death, myocardial infarction, stroke, heart failure, thromboembolic events, thrombosis of vascular access
- Cardiomyopathy
- Pulmonary artery hypertension
- Cancer-related mortality and tumor progression and recurrence
- Esophageal and gastric erosions
- Proliferative retinopathy, macular edema, choroidal neovascularization
- Exacerbation of rheumatoid arthritis

Any relevant AE should be recorded in the relevant section of the subject's eCRF.

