**Other disease-related criteria**

9. Liver disease (if any of the following occurs):
  - (Screening verification only): Alanine transaminase (ALT) >2×upper limit of normal (ULN)
  - (Screening verification only): Bilirubin >1.5×ULN (isolated bilirubin >1.5×ULN is acceptable if bilirubin is fractionated and direct bilirubin is <35%)
  - Current unstable active liver or biliary disease (generally defined by the onset of ascites, encephalopathy, coagulopathy, hypoalbuminemia, esophageal/gastric varices, persistent jaundice, or cirrhosis)

Note: Stable liver disease (including asymptomatic gallstones, chronic hepatitis B/C, or Gilbert's syndrome) is acceptable if the subject otherwise meets entry criteria.
10. Malignancy: History of malignancy within 2 years prior to screening, or currently receiving treatment for cancer, (PD patients only) complex renal cystic >3 cm (II F, III or IV based on the Bosniak classification)

Note (ND patients and PD patients): The only exception is squamous cell or basal cell carcinoma of the skin that has been definitively treated ≥ 8 weeks before screening.

11. In the opinion of the investigator, Hgb increase to the target range (11.0-13.0 g/dL) is medically risky.

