#### **5.4. Withdrawal/Dropout Criteria**

If subjects meet one of the following criteria, study treatment should be permanently discontinued and subjects will be withdrawn from the study. The withdrawal reason should be recorded.

- Hgb <7.5 g/dL  
Note: HemoCue Hgb values will be employed. If an initial Hgb value meets the Hgb stopping criteria, measurement will be repeated at the same study visit (using the same sample) to calculate the average. If the average meets the Hgb stopping criteria, study treatment will be discontinued.
- Subject needs for maintenance dialysis or changes dialysis modality (PD subjects only) during the study period.
- Kidney transplant
- Subject becomes pregnant or intends to become pregnant during the study.
- Diagnosis of new or recurrent cancer

- Liver chemistry abnormalities exceeding the threshold criteria (see Section 5.4.1.)
- Need for chronic (more than 14 days) use of prohibited medication (strong inhibitors/ inducers of CYP2C8 meet this criteria)
- When the investigator (or subinvestigator) considers necessary to withdraw the subject from the study for other reasons

Subjects who meet any of the withdrawal criteria or are withdrawn for other reasons during the treatment phase should be assessed at withdrawal visit after study treatment is discontinued, and will then enter the follow-up phase.

Should a subject fail to attend a required study visit, the investigator (or subinvestigator) should take the following measures:

[figure not shown]
- The investigator (or subinvestigator) or designee should attempt to contact the subject and reschedule the missed visit as soon as possible.
- The investigator (or subinvestigator) should counsel the subject on the importance of maintaining the assigned visit schedule and determine whether the subject is willing to continue his/her participation in the study and/or whether the subject should remain in the study.
- The investigator (or subinvestigator) or designee should make every effort to regain contact with a subject who is deemed “Lost to Follow-up”. All efforts to contact the subject should be documented in the subject’s clinical charts.
- Should the subject continue to be unreachable, then and only then will he/she be considered “Lost to Follow-up.”

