##### **9.4.4.2. Adverse Events**

All AEs will be categorized by the MedDRA system organ class and preferred term to tabulate the number and incidence. All AEs, SAEs, AEs leading to discontinuation of study treatment, and AEs of special interest will be summarized separately. Similar summary will be provided for study treatment-related AEs.

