Cancer-related mortality, tumor progression and recurrence	
In clinical trials, use of rhEPO in patients with cancer has been associated with increased risk of cancer related morbidity and mortality.
 
Administration of 60 mg/kg GSK1278863 to mice caused minimal increases in circulating VEGF while significant EPO increases were observed.
 
In clinical studies up to 4 weeks duration, a dose-ordered increase in VEGF plasma concentrations, an angiogenic factor that has been implicated in tumor growth, was observed at doses ranging from 10 to 150 mg. In clinical studies up to 24 weeks duration at doses up to 25 mg, changes in VEGF plasma concentrations were variable but similar relative to control.
 
Following review of clinical data received to date, this has not been identified as a safety concern for GSK1278863.
	
 
• Specific eligibility criteria related to personal history of malignancy are outlined in Section 5.2..
 
▲ Stopping criteria for subjects with treatment emergent malignancy are outlined in Section 5.4.
 
▲ These risks have been identified as AEs of special interest and will be monitored instreamly by the internal safety review team throughout the study period.
 

Pulmonary artery hypertension (PAH)	
 
• A role for HIF-regulated pathways in the pathophysiology of PAH has been suggested based on well established effects of acute and chronic hypoxia in man on the pulmonary vasculature (vasoconstriction), and by findings in patients with naturally occurring mutations that result in decreased HIF degradation (Smith, 2006; Formenti, 2011).
 
• There have been no histopathologic findings suggestive of PAH in pre-clinical safety studies (up to 13-weeks duration in mice and dog, up to 26-weeks in rat, and up to 39-weeks in monkeys).
 
• Acute hypoxic challenge (rats): GSK1278863A produced increases in peak right ventricular pressure (PRVP) during acute hypoxia that were slightly higher than the vehicle control group. These hypoxia-induced PRVP changes fall within the range of PRVP differences
 
	
 
▲ These risks have been identified as AEs of special interest and will be monitored instreamly by the internal safety review team throughout the study period.
 

Potential Risk of Clinical Significance	Summary of Data/Rationale for Risk	Mitigation Strategy

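### The cancer adverse event of special interest leaves out new malignancy, which Section 5.4 and Appendix 2 treat as part of the same risk

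*Protocol*

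**What the plan says.** All references are to the Protocol, Amendment 4.

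- **Section 7.4.2** lists the AESIs that investigators must detect, document and report. The cancer item reads "Cancer-related mortality and tumor progression and recurrence".
- **Section 12.2, Appendix 2** carries the same three elements as its risk heading: "Cancer-related mortality, tumor progression and recurrence". The mitigation column of that row says "Stopping criteria for subjects with treatment emergent malignancy are outlined in Section 5.4", and has the internal safety review team monitor the risk during the study as an AESI.
- **Section 5.4** includes "Diagnosis of new or recurrent cancer" among the criteria under which "study treatment should be permanently discontinued and subjects will be withdrawn from the study".
- **Section 5.2, criterion 10** excludes "History of malignancy within 2 years prior to screening, or currently receiving treatment for cancer". It adds: "The only exception is squamous cell or basal cell carcinoma of the skin that has been definitively treated", with treatment at least 8 weeks before screening.
- **Section 9.4.4.2** plans tables of all AEs and SAEs, and states that "AEs leading to discontinuation of study treatment, and AEs of special interest will be summarized separately".
- **Section 7.4.1.3** requires follow-up to resolution, stabilization or another explanation for all SAEs, and for non-serious events only if they are AESIs.

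**The concern.** The protocol gives one risk two scopes. For stopping treatment and for mitigation, the cancer risk includes a new malignancy. For AESI reporting it includes only death from cancer, progression and recurrence.

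The narrower scope suits patients with a known tumor, whom criterion 10 largely keeps out. Appendix 2 also cites a growth factor linked to tumor growth. In a subject with no known cancer, faster growth of an undetected tumor would first show as a new diagnosis, and that is the category left out.

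The AESI table is where a reader of pivotal data would look for the cancer risk. Built to the letter of Section 7.4.2, its cancer row could be at or near zero in both arms even if several subjects were newly diagnosed, and could be taken as reassurance.

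**Working it through.** **Wording check.** Does each event belong to the cancer risk in each place?

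| Event | 7.4.2 and Appendix 2 heading | 5.4 withdrawal | Appendix 2 mitigation |
|---|---|---|---|
| Cancer death | yes | not named | not named |
| Progression | yes | not named | not named |
| Recurrence | yes | yes | not named separately |
| New malignancy | **no** | yes | yes |

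The finding rests on the last row. The arithmetic below only gives its scale.

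**Exposure base.** The plan's figure reproduces: 100 completers per group / (1 - 0.30) = 142.9, so 143 per group and 286 in total. Assume a constant dropout hazard reaching 30% at 52 weeks, and 4 weeks of follow-up for everyone:

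- hazard = -ln(0.70) = 0.357 per year
- on treatment: 143 x 0.30 / 0.357 = about 120 person-years per arm
- follow-up: 143 x 4/52 = 11 person-years
- total: about 131 person-years per arm

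**Assumed rates (none is in the documents).** New cancer 0.5 to 2 per 100 person-years; 2% to 10% of subjects with an earlier cancer; recurrence in those subjects 1 to 5 per 100 person-years.

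- New cancers per arm: 131.3 x 0.005 = 0.66, to 131.3 x 0.02 = 2.6. Both arms: 1.3 to 5.3.
- Recurrences per arm: 131.3 x 0.02 x 0.01 = 0.03, to 131.3 x 0.10 x 0.05 = 0.66.
- Chance of no recurrence in either arm, exp(-2 x expected per arm): 95% at the low end and 27% at the high end. With 5% having a history and 2 recurrences per 100 person-years, the expectation is 0.131 per arm and the chance is 77%.

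**Share omitted** = new / (new + recurrent). Exposure cancels.

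- Lowest: 0.005 / (0.005 + 0.10 x 0.05) = 50%
- Highest: 0.02 / (0.02 + 0.02 x 0.01) = 99%
- A narrower set (new cancer 1 to 3 per 100 person-years, 5% to 10% with a history, recurrence 1 to 3 per 100 person-years) gives 0.01 / 0.013 = 77% to 0.03 / 0.0305 = 98%.

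The share therefore depends on the inputs chosen. The count also leaves out cancer death or progression in a newly diagnosed subject, which would enter the AESI row as worded.

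**What the fix could show.** With 143 per arm and a control risk of 0.5%, 1% or 2%, Fisher's exact test has power of 0.2%, 2% or 8% for a doubling of risk.

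**The case against.** The strongest reply is that nothing is lost. Malignant cancers are given as an example of an SAE in Section 12.6.2. A new cancer on treatment forces discontinuation under Section 5.4, so it should also reach the discontinuation-AE table by arm, and SAEs are followed to resolution or stabilization. The withdrawal reason is recorded, and reasons for discontinuation are a safety endpoint. All of this stands. A reader might infer that the AESI row is the only planned count of new cancers, or that such cancers go unrecorded or unfollowed; the protocol does not support either reading.

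A reader might also infer that the population is free of cancer and the row therefore empty. That is too strong. The look-back is 2 years, so older cancers and treated skin carcinomas can enter and recur. Sparse is the most that can be said.

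A third reply is that Section 7.4.2 gives risk headings and that the Reporting and Analysis Plan (RAP), which is not shown, decides which dictionary terms fill each row. This stands in part. Term mapping does belong to the RAP and may turn out broader. But the list in Section 7.4.2 is a stated definition that investigators report against, and the follow-up rule depends on it. A RAP that counted new malignancies would be wider than the protocol's own list.

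Finally, the heading follows the evidence cited in Appendix 2 on erythropoietin in patients with cancer, and the mismatch may be loose drafting. That explains the wording but does not reconcile it with Section 5.4.

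**Conclusion.** The inconsistency is real and can be read directly from the text: new malignancy belongs to the cancer risk in Section 5.4 and in the Appendix 2 mitigation column, but not in the AESI item or the Appendix 2 heading. Three things follow: first diagnoses fall outside the dedicated AESI summary, outside the safety team's review of AESIs as worded, and, when non-serious, outside the follow-up in Section 7.4.1.3. The last gap is probably small, since malignant cancers would usually be reported as SAEs.

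No share of missed cancers can be stated as fact. Under the assumed rates it runs from about half to nearly all. No planned test or efficacy conclusion changes, and the corrected summary would still hold only a few events per arm. This is a cheap improvement to the safety reporting, not a flaw that undermines the trial.

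**What to change.** In Section 7.4.2 and in the matching Appendix 2 risk heading, put 'New malignancy' in front of the three elements already there. The AESI table in Section 9.4.4.2 would then count treatment-emergent malignancies by arm, and the item would agree with Section 5.4 and the mitigation column.

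The cost is one line in two places and a wider term list in the RAP. The events are already collected as AEs or SAEs, so no visit or test is added. The small downside is that non-serious new cancers would also need to be followed under Section 7.4.1.3.
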